### **18.5.3. Documentation**

All premedication(s) administered will be reported on the appropriate eCRF.

## **18.6. Appendix F: Restrictions Relating to COVID-19**

This section describes safety measures that were taken due to the COVID-19 pandemic. These measures will also apply to subsequent outbreaks/pandemics resulting from SARS-CoV-2 infections.

### **18.6.1. Restrictions to Study Conduct**

The following will be taken into consideration when determining whether there are any restrictions to conducting onsite visits:

- Local government/institution and hospital readiness to allow clinical research activities
- Confirmed absence of COVID-19-related restrictions on mobility of persons (central, regional, & municipal government plus institutional) applicable to the trial candidates, subjects, or site personnel
- Ability for clinical research associate (CRA) to perform onsite routine monitoring in accordance with the Monitoring Plan.
- Confirmed ability to perform research PFT per protocol/established guidelines
- Confirmed ability to perform research HRCT per protocol/established guidelines
- Confirmed ability to process and ship central and local laboratory samples per protocol/established guidelines
- Adequate stock of study supplies including laboratory kits, personal protective equipment, and study treatment preparation and administration materials
- Unrestricted courier services

The Investigator will be responsible for determining if it is safe to proceed with onsite study visits at his/her site considering the requirements above. If the Investigator determines that onsite study procedures are not feasible based on the criteria above, they must inform the IRB/IEC and advise the CRA or clinical trial lead (CTL). Recommendations for how to proceed if there are restrictions preventing onsite visits are included Section [18.6.2](#).

To resume onsite study visits, the Investigator must inform the IRB/IEC and CRA or CTL after considering the guidelines above.

### **18.6.2. Study Visit Guidelines**

#### **18.6.2.1. Consenting and Screening**

When study procedures cannot be performed onsite, the Investigator should pause consenting of new subjects and suspend screening procedures for already consented subjects. Subjects who have been consented but have not received study treatment, should be considered screen failures (with the option to rescreen at a later time). If the Investigator believes these activities may resume after considering the guidelines in Section [18.6.1](#), the Investigator must inform the IRB/IEC and CRA or CTL.

### **18.6.2.2. Managing Treatment Period Study Visits**

When onsite study procedures cannot be performed for already randomized subjects, up to 2 scheduled Treatment Period visits may be conducted remotely. The implementation of remote visits allows for a maximum delay in study treatment administration of 6 weeks after the last dose. Section 18.6.2.4 describes what data should be collected at a minimum during a remote visit.

If onsite visits can resume and study treatment can be administered  $\leq$  6 weeks after the last dose, feasible study-related procedures should resume onsite as soon as possible per Section 12.2. In this case, the subject should proceed with the next protocol visit and follow those procedures. For example, if the subject has remote Visit 4 and Visit 5, and onsite visits can resume within 6 weeks of their last dose of study treatment, the subject will resume the study and complete Visit 6 study procedures.

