#### **11.1.2. Safety Laboratory Tests**

Safety laboratory tests will include the following:

Central laboratories will be used for clinical laboratory tests, although local testing may be used for emergencies and for hemoglobin for DLCO correction. Details regarding specimen collection and processing will be provided in the Lab Manual. Safety laboratory tests will be analyzed throughout the study.

Blood samples and urine samples will be collected for clinical laboratory testing as shown in [Table 1](#). If needed, additional blood samples may be taken for DLCO correction. See Section [8.4.5](#) for guidance on how to manage subjects with elevations in transaminases.

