#### 12.2.4. Visits 5, 7, 9, 11, and 13 (Days 43, 71, 99, 127, 155) All Subjects

Each of Visits 5, 7, 9, 11, and 13 will be conducted  $14 \pm 7$  days after the previous dose of study treatment. The following study procedures will be performed at these visits **before** the study treatment infusion:

- Record AEs and the status of previously unresolved AEs.
- Record concomitant medications.
- [REDACTED]
- Administer premedications, if applicable (see Section 18.5).
- Measure vital signs (systolic and diastolic blood pressure, heart rate, respiration rate, and oral temperature) and SpO2 once before the study treatment infusion (if premedication is administered, vital signs should be measured after premedication).
- Administer assigned study treatment.

The following study procedures will be performed at these visits **during** the study treatment infusion:

- Measure vital signs (systolic and diastolic blood pressure, heart rate, respiration rate, and oral temperature) and SpO2 midinfusion  $\pm$  5 minutes (if infusion is administered at a modified rate [REDACTED] the timing should correspond to the middle of the modified infusion duration).

The following study procedures will be performed at these visits **after** the study treatment infusion:

- Measure vital signs (systolic and diastolic blood pressure, heart rate, respiration rate, and oral temperature) and SpO2 within 15 minutes after the end of the study treatment infusion.

[REDACTED]

[REDACTED]

Refer to Section 18.6 for guidance on clinical trial conduct relating to COVID-19.

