#### **12.2.5. Visits 6, 8, 10, and 12 (Days 57, 85, 113, and 141) All Subjects**

Each of Visits 6, 8, 10, and 12 will be conducted 14  $\pm$  7 days after the previous dose of study treatment. The following study procedures will be performed at these visits **before** the study treatment infusion:

- Record AEs and the status of previously unresolved AEs.
- Record concomitant medications.
- Collect urine sample for urine pregnancy test (female subjects of childbearing potential only)
- [REDACTED]
- Collect blood for the following tests:
  - chemistry
  - hematology

- [REDACTED]
- [REDACTED]
- [REDACTED]
- [REDACTED]
- [REDACTED]

- Administer premedications, if applicable (see Section 18.5).
- Measure vital signs (systolic and diastolic blood pressure, heart rate, respiration rate, and oral temperature) and SpO2 once before the study treatment infusion (if premedication is administered, vital signs should be measured after premedication).
- Administer assigned study treatment.

The following study procedures will be performed at these visits **during** the study treatment infusion:

- Measure vital signs (systolic and diastolic blood pressure, heart rate, respiration rate, and oral temperature) and SpO2 midinfusion  $\pm$  5 minutes (if infusion is administered at a modified rate [REDACTED], the timing should correspond to the middle of the modified infusion duration).

The following study procedures will be performed at these visits **after** the study treatment infusion:

- Measure vital signs (systolic and diastolic blood pressure, heart rate, respiration rate, and oral temperature) and SpO2 within 15 minutes after the end of the study treatment infusion.

Refer to Section 18.6 for guidance on clinical trial conduct relating to COVID-19.

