### **18.6.2.4. Data Collection During Remote Visits**

During remote visits, the following information should be collected at a minimum:

1. Concomitant medications
2. Adverse events (If the subject reports COVID-19, ask whether the infection has been confirmed via testing. If possible, the test used should be recorded.)

3. Vital signs (Has the subject been febrile? If so, how was this detected?)
4. Pulse oximetry and supplemental oxygen requirement (if subject has equipment at home)

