**Appendix 2: Schedule of visits**

Visit	Screening a		Treatment Period					EOT	Follow-Up		
	1a	1b	2	3	4	5, 7, 9, 11, 13 (Simple tests)	6, 8, 10, 12 (Detailed tests)	14 (or ET)	15	16	
Week	-6 to -1		0	2	4	6, 10, 14, 18, 22	8, 12, 16, 20	24 (2 wk postdose)	28 (4 wk post V14/ET)	34 (10 wk post V14/ET)	
Study Day	-42 to -7		1	2	15	29	43, 71, 99, 127, 155	57, 85, 113, 141	169	197	239
Allowable Window (days) b					± 4	± 7	± 7	± 7	± 7	± 7	± 7
Study Procedure											
Informed Consent	X c										
Eligibility	X	X	X								
Demographics and baseline characteristics	X										
Medical history	X										
Adverse events	X d	X	X	X e	X	X	X	X	X	X	X
IPF history and previous treatments	X										
Prior medications	X										
Concomitant medications	X d	X	X	X e	X	X	X	X	X	X	X
Physical examination (complete)	X							X			
Physical examination (abbreviated) f		X	X								
Height	X										
Weight	X							X			
12-lead ECG	X	X				X g		X			
Vital signs h	X	X	X	X	X	X	X	X	X	X	X
Chemistry	X		X		X	X		X	X		X
Hematology	X	X n	X			X		X	X	X n	X
Urinalysis	X							X			X
Pregnancy test (urine) for WCBP o	X		X			X		X	X	X	X
Serology (HCV Ab, HBsAg, HIV 1/2)	X										
SARS-CoV-2 test f	X										
Randomization			X								

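### On the legible text, when the last remote visit is Visit 4, 6, 8, 10 or 12, Protocol 18.6.2.2 restarts dosing with no required chemistry, hematology or urine pregnancy test

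*Protocol*

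**What the plan says.** **Restart rule (Protocol 18.6.2.2).** At most two treatment-period visits may be remote, and the gap since the last dose may not exceed 6 weeks. The section first says that feasible procedures return to the site promptly under Section 12.2. It then fixes what is done: "In this case, the subject should proceed with the next protocol visit and follow those procedures". Its only example has Visits 4 and 5 remote, after which "the subject will resume the study and complete Visit 6 study procedures".

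**Remote visits (Protocol 18.6.2.4).** "During remote visits, the following information should be collected at a minimum": concomitant medications, adverse events, vital signs, and oximetry if the subject has the equipment. No laboratory test is listed.

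**Where samples are due.** Protocol 12.2.3 (Visit 4) and 12.2.5 (Visits 6, 8, 10, 12) list chemistry, hematology and the urine pregnancy test before the infusion. For Visits 5, 7, 9, 11 and 13, Protocol 12.2.4 says "The following study procedures will be performed at these visits" before the infusion. Its legible items are adverse events, concomitant medications, optional premedication, vital signs with SpO2, and the dose. One item is redacted. SAP Appendix 2 leaves the simple-tests column empty in the chemistry, hematology and pregnancy rows. It marks chemistry, but not hematology, at Visit 3.

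**Laboratory logistics.** Protocol 11.1.2 says: "Central laboratories will be used for clinical laboratory tests, although local testing may be used for emergencies". Protocol 18.6.1 lists among the matters to weigh before onsite visits: "Confirmed ability to process and ship central and local laboratory samples per protocol/established guidelines".

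**Use of the data.** SAP 3.4.7 limits post-baseline laboratory summary tables to scheduled visits. SAP 6.1 lets unscheduled values enter the worst-grade shift tables and lets them fill a nominal visit that has no measurement. SAP 7.6.3 adds a Hy's Law count and eDISH plots.

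**The concern.** The restart rule replaces the missed visit with the next one and does not carry over what the missed visit would have collected. Laboratory visits alternate with simple-tests visits from Visit 4 on. If the last remote visit is a laboratory visit, the subject therefore returns to a visit with no scheduled panel and is infused there. The published example ends on a simple-tests visit and returns to a laboratory visit, so it does not show the problem.

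The primary objective is safety. Protocol 14.5 makes clinically relevant laboratory deterioration an adverse event, so a silent change during the gap enters the primary endpoint only if a sample is taken. A sample before the restart dose would show whether an abnormality came before or after that dose, and would arrive 14 days before the next planned panel. Background nintedanib or pirfenidone may continue through the gap, and causality is assessed against it as well as study drug. The pregnancy test is lost in the same way, although pregnancy requires stopping treatment (Protocol 8.4.1).

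**Working it through.** The plan states no figure for this path, so there is none to reproduce. The check applies the restart rule to the nominal calendar.

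**Inputs**
- Nominal days (Protocol Table 1): V2 = 1, V3 = 15, V4 = 29, V5 = 43, V6 = 57, V7 = 71, V8 = 85, then every 14 days to V14 = 169.
- Hematology at V2, 4, 6, 8, 10, 12 and 14 (Protocol 12.2.3, 12.2.5, 12.3; SAP Appendix 2). Chemistry at the same visits, plus V3 if SAP Appendix 2 is followed.
- Samples are drawn before that visit's infusion.

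**Formulas**
- Age at restart = day of restart visit − day of last sample.
- Interval = day of next required sample − day of last sample.
- Infusions between samples = doses given from the last sample up to the next.

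**Which patterns are affected.** One unbroken run of one or two remote visits among V3 to V13 gives 11 singles + 10 pairs = 21. Those that include V4, 6, 8, 10 or 12: 5 singles + 10 pairs = 15. Of these 15:
- 10 end on a laboratory visit and restart with no required panel: singles 4, 6, 8, 10, 12 and pairs 3-4, 5-6, 7-8, 9-10, 11-12.
- 4 restart at a laboratory visit: 4-5, 6-7, 8-9, 10-11.
- 1 (12-13) goes to Visit 14, which has samples and no dose.

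These are counts of patterns, not frequencies. Two separate single remote visits also fit the allowance and were not counted.

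**Size (hematology)**

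| Case | Age at restart infusion | Interval | Infusions between samples | Gap since last dose |
|---|---|---|---|---|
| On schedule (V4 to V6) | 43 − 29 = 14 | 57 − 29 = 28 | V4, V5 = 2 | 14 |
| Pair 5-6 remote | 71 − 29 = 42 | 85 − 29 = 56 | V4, V7 = 2 | 71 − 29 = 42 |
| Single V6 remote | 71 − 29 = 42 | 85 − 29 = 56 | V4, V5, V7 = 3 | 71 − 43 = 28 |
| Single V4 remote | 43 − 1 = 42 | 57 − 1 = 56 | V2, V3, V5 = 3 | 43 − 15 = 28 |

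For the on-schedule row, age is that at the simple-tests visit. The 42-day age and 56-day interval hold in all 10 patterns. Chemistry is the same, with one exception: after a single remote Visit 4 with chemistry drawn at Visit 3, age is 43 − 15 = 28 and interval 57 − 15 = 42.

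**Time off drug.** Protocol 14.2.1 expects 2 weeks to exceed five terminal half-lives. On that basis about 42 − 14 = 28 days of a two-visit gap, and 28 − 14 = 14 days of a single-visit gap, are off drug.

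**With a make-up sample at V7.** The 56-day interval splits into 71 − 29 = 42 and 85 − 71 = 14. Infusions before that sample fall to 1 for the pair (V4) and 2 for the single (V4, V5), the planned number.

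**The case against.** **Redactions.** Much that could hold a restart or liver-monitoring rule is blacked out: most of Protocol 8.4.5, all of 10.2.2.1 on dose administration, a bullet in 8.4.1, the test list in 11.1.2, and rows and footnotes of Table 1. This stands as a limit. The legible chemistry, hematology and pregnancy rows make a scheduled panel at the simple-tests visits unlikely, but they cannot exclude a restart rule elsewhere.

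**The sentence on feasible procedures** in 18.6.2.2 might be read as permission to catch up. It points to Section 12.2, and the next sentence limits the content to the next visit's procedures. It does not require a make-up draw.

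**Calendar time overstates the exposure.** This stands. Dosing paused too, and for two-visit gaps the infusions between hematology samples are the planned 2. Those gaps also sit exactly on the 42-day limit, so any lateness after the last dose bars the restart.

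**Other safeguards exist.** Adverse events and vital signs are collected remotely and at restart, with SpO2 at restart. The Investigator may order unscheduled tests (Section 12), and the remote data set is only a minimum. The Data Monitoring Committee reviews safety laboratory data and may meet ad hoc. These reduce the risk, but none requires the sample.

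**Dosing without a same-day panel is already the design** at simple-tests visits. True, but there the preceding panel is due 14 days earlier. Here it was missed.

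**Conclusion.** The point holds on the legible text as a modest safety-monitoring gap in a contingency path. When the last remote visit is Visit 4, 6, 8, 10 or 12, following 18.6.2.2 exactly gives an infusion with no required chemistry, hematology or pregnancy test. Hematology is nominally 42 days old instead of 14, and the sampling interval is 56 days instead of 28. Infusions between hematology samples rise from 2 to 3 only for single-visit gaps. This rests on nominal days (visit windows shift them), on one unbroken run of remote visits, and on no restart rule lying under the redactions. How often it happens cannot be known from the documents.

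A reader might infer more, and the documents do not support it:
- *That every interruption has this gap.* Four of the 15 patterns return to a laboratory visit, and one goes to Visit 14 with no dose.
- *That the risk doubles because the interval doubles.* Much of the added time is off drug.
- *That a make-up sample would stop dosing on an abnormality.* Routine tests go to a central laboratory, so this is true only if the result is awaited.
- *That the arms would be compared unfairly.* The rule is the same in all arms, so bias is probably small.
- *That the protocol has no restart safeguard at all.* The redactions prevent that conclusion.

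**What to change.** Add to Protocol 18.6.2.2: *Chemistry, hematology and, where applicable, the urine pregnancy test missed at the last remote visit are collected before the infusion at the first onsite visit.*

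Record the sample at its true date, at the restart visit or as unscheduled, and not under the missed nominal visit. State in SAP 3.4.7, 6.1 and 7.6.3 that it counts in the worst-grade shift tables, the Hy's Law count and the eDISH plots, but does not fill the missed visit's by-visit summary. The exclusion matters. A Day 71 sample lies outside the Visit 6 window (Day 57 ± 7, so Days 50 to 64) and may be 42 days after the last dose, whereas that summary is meant for values about 14 days after a dose. The fill-in rule in SAP 6.1 could otherwise place it there if it is recorded as unscheduled.

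Awaiting the result before dosing stays optional. A sponsor who wants it could use a local test, or draw the sample some days earlier, which Section 12 already allows for assessments not tied to the infusion. Either adds a trip or a local test.

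The cost is a short amendment to Appendix F with IRB/IEC approval (Protocol 16.8), a short SAP addition, and a slightly longer restart visit. The samples were already planned, the subject is on site, and the ability to ship samples is already weighed before onsite visits resume.

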### **18.6.2.3. Managing End-of-Treatment and Follow-Up Period Visits**

#### **Subjects Who Complete Planned Treatment Period Visits**

If a subject completes all planned Treatment Period visits, remote or onsite through Visit 13, Visit 14 should be conducted per Section 12.3. If it is not safe or feasible to proceed onsite, Visit 14 may be postponed for up to 8 weeks after the last dose. If onsite Visit 14 will not be safe or feasible in  $\leq$  8 weeks after the last dose, the visit should be conducted remotely. If at any time circumstances change and it becomes safe and feasible for a subject to come to the site, subsequent visits should be performed onsite and follow procedures per Section 12 for the visits described below.

- a. Visit 14 performed onsite or remotely  $\leq$  8 weeks after Visit 13
- b. Visit 15 performed onsite or remotely  $4 \pm 1$  week after Visit 14
- c. Visit 16 performed onsite or remotely  $10 \pm 1$  week after Visit 14

#### **Subjects Who Do Not Complete Planned Treatment Period Visits**

If a subject misses 2 Treatment Period visits as described in Section 18.6.2.2, and it is not expected that study treatment administration can restart  $\leq$  6 weeks after the last dose, perform a remote ET visit. If circumstances change and it becomes safe and feasible for the subject to come to the site, ET and Follow-Up visits should be performed onsite and follow procedures per Section 12.

- a. ET visit performed onsite or remotely  $2 \pm 1$  week after the second missed visit
- b. Visit 15 performed onsite or remotely  $4 \pm 1$  week after ET visit
- c. Visit 16 performed onsite or remotely  $10 \pm 1$  week after ET visit

### **18.6.2.4. Data Collection During Remote Visits**

During remote visits, the following information should be collected at a minimum:

1. Concomitant medications
2. Adverse events (If the subject reports COVID-19, ask whether the infection has been confirmed via testing. If possible, the test used should be recorded.)

3. Vital signs (Has the subject been febrile? If so, how was this detected?)
4. Pulse oximetry and supplemental oxygen requirement (if subject has equipment at home)

#### **18.6.2.5. High-Resolution Computed Tomography**

#### **18.6.3. Analysis Related to COVID-19**

Additional sensitivity analyses may be performed due to the COVID-19 pandemic. All analyses related to COVID-19 will be conducted in accordance with regulatory guidelines. These analyses will be described in the SAP.

#### **18.6.4. Clinical Study Report**

The CSR will include information specific to the COVID-19 pandemic consistent with regulatory guidelines.

## Statistical Analysis Plan

Sponsor Name: Nitto Denko Corporation  
Sponsor Protocol ID: ND-L02-s0201-005

### Glossary of Abbreviations

Abbreviation	Term
████	████████████████████
AE	Adverse event
AEOI	Adverse events of special interest
AIC	Akaike's information criterion
ALP	Alkaline phosphatase
ALT	Alanine aminotransferase
ANCOVA	Analysis of covariance
AR(1)	First-order autoregressive
AST	Aspartate aminotransferase
ATC	Anatomical Therapeutic Chemical
████	████████████████████
bpm	beats per minute
CI	Confidence Interval
COVID-19	Coronavirus disease
CS	Compound symmetry
CTCAE	Common Terminology Criteria for Adverse Events
DLco	Diffusion capacity of the lung for carbon monoxide
ECG	Electrocardiogram
eCRF	Electronic case report form
EDC	Electronic data capture
eDISH	Evaluation of drug induced serious hepatotoxicity
EOT	End-of-Treatment
ET	Early Termination
FEV1	Forced expiratory volume in 1 second
FVC	Forced vital capacity
████	████████████████████
HRCT	High-resolution computed tomography
ILA	Interstitial lung abnormalities
ILD	interstitial lung disease
IPF	Idiopathic pulmonary fibrosis
ITT	Intention-to-treat
IV	Intravenous
IWRS	Interactive Web Response System
████	████████████████████
KW	Kruskal-Wallis
KM	Kaplan-Meier
LLN	Lower Limit of Normal
MedDRA	Medical Dictionary for Regulatory Activities

### Statistical Analysis Plan

Sponsor Name: Nitto Denko Corporation  
Sponsor Protocol ID: ND-L02-s0201-005

Abbreviation	Term
NCI	National Cancer Institute
PD	Pharmacodynamics
PFT	Pulmonary function testing
████	██
PK	pharmacokinetic(s)
PP	Per protocol
████	██
Q2W	Every 2 weeks
QLF	Quantitative lung fibrosis
QOL	Quality of life
QTcF	QT interval corrected using Fridericia's formula
SAE	Serious Adverse Event
SAF	Safety Population
SAP	Statistical Analysis Plan
SD	Standard Deviation
████	██
SLB	Surgical lung biopsy
SOC	System Organ Class
SpO 2	Peripheral capillary oxygen saturation
TEAE	Treatment-emergent adverse event
TFLs	Tables, Figures and Listings
TOEP	Toeplitz
UIP	Usual interstitial pneumonia
ULN	Upper limit of normal
VA	Alveolar volume
WBC	White blood cell
WHO	World Health Organization
████	██

